Structural Types of the Foot and Their Influence on Core and Sports Performance in College
Athletes

NCT ID not yet assigned

Date: 25/August/2022

Structural Types of the Foot and Their Influence on Core and Sports Performance in College Athletes

General Objective:

The objective of this study is to assess the impact of foot arch height and the implementation of a corrective exercise program on foot posture alterations in college athletes. The evaluation will focus on three aspects: postural stability, muscular activity at the center of gravity, and sports performance. This assessment will be conducted using advanced measurement systems such as Surface Electromyography, motion analysis technology, Ergospirometry, and body motion kinematics measurement systems. The findings of this study aim to contribute to the optimization of athlete training and overall performance.

Specific Objectives:

1. Compare the average muscular activity at the center of gravity and both static and dynamic stability among college athletes with low, high, and neutral foot arches. This analysis will employ Surface Electromyography and a 3D motion measurement system. The goal is to determine the potential influence of different foot structural types on core muscle activity and overall stability in athletes.
2. Assess the potential variations in jump force, acceleration, step speed, race time, maximum oxygen consumption, and anaerobic threshold among college athletes with high, low, or neutral foot arches. This investigation will utilize biomechanical analysis technology and Ergospirometry, with the aim of identifying any possible impact of varying foot structural types on athletes' performance capacity.
3. Evaluate the potential changes in terms of center of gravity muscle activity and both static and dynamic stability after a 12-week exercise program designed to correct different foot structural types (high or low) in college athletes. This assessment will employ Surface Electromyography and a 3D motion measurement system, with the objective of establishing the effectiveness of these exercises in improving athletes' body stability.

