4. Determine the potential alterations in VO₂max, anaerobic threshold, jump force, acceleration, step speed, and race time in college athletes, following a 12-week exercise program aimed at correcting two foot structural types (high or low). This investigation will use Ergospirometry and a 3D motion kinematics assessment system to evaluate possible improvements in sports performance resulting from the exercise program.

Methodology:

Design and Sample: An observational study design was employed to assess the impact of foot structural types on postural stability, activity of core stabilizing muscles, maximum oxygen consumption (VO₂max), anaerobic threshold, and lower limb performance in male college athletes over 18 years old from the University of Magdalena, participating in various sports modalities such as rugby, soccer, basketball, volleyball, tennis, table tennis, karate, and cheerleading. For evaluating the effects of a corrective exercise program targeting high or low foot posture alterations on the same variables, an experimental design was used. Stratified random sampling was employed for convenience, and 35 participants with low medial arch, 32 with high arch, and 36 with neutral arch were selected for the observational studies. For the experimental studies, 33, 31, and 33 participants were selected, respectively, from a pool of 230 candidate athletes. G Power 3.1.9.7 software was used to determine the appropriate sample size, considering three independent groups, an alpha level set at 0.05, a power (1-β) of 0.80, and an effect size (f) of 0.40.

Foot Type Evaluation: The Foot Arch Index, which determines the medial arch height by measuring the ratio between the midfoot area and the total foot area (excluding toes), was used to evaluate the foot type. An index less than 0.21 indicated a high-arched foot, an index greater than 0.26 indicated a flat foot, and an index between 0.21 and 0.26 was considered a "neutral" arch. Participants' footprints were obtained using a washable ink pad, and analysis software was used to calculate the Foot Arch Index.

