Statistical Analysis: Data were reported as mean \pm standard deviation and analyzed using IBM SPSS Statistics (version 21, IBM Corp., NY, USA). The normality of each variable for different foot types (low, high, or neutral) was checked using the Shapiro-Wilk test. The significance of variables such as age, weight, height, and muscle/fat percentages among the three foot types was evaluated using ANOVA if the variables followed a normal distribution, or the Kruskal-Wallis test if they did not. For descriptive studies, ANOVA was used for normally distributed dependent variables or Kruskal-Wallis for non-normally distributed variables. Levene's test was used to assess homogeneity of variances. Post-hoc analysis with Bonferroni correction was performed to determine differences between groups. Pearson's or Spearman's correlation was used to assess the relationship between variables. For experimental studies, the effects of exercise on dependent variables were assessed using repeated-measures ANOVA or Friedman's test. Levene's test was used for variance homogeneity. Post-hoc analysis with Tukey correction was conducted to assess pre-post exercise significances of dependent variables. Eta-squared (η^2_p) or Kendall's W concordance coefficient was used to evaluate the effect size of the exercise program on foot types. The significance level for both studies was set at $p \leq 0.05$.

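### Objectives 3 and 4 have no primary outcome, no list of the outcomes tested and no error control across outcomes

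*Combined protocol and SAP*

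**What the plan says.** Under Statistical Analysis, the observational part is handled one variable at a time: "For descriptive studies, ANOVA was used for normally distributed dependent variables", with Kruskal-Wallis otherwise. In the experimental part, "the effects of exercise on dependent variables were assessed using repeated-measures ANOVA" or Friedman's test. One threshold covers everything: "The significance level for both studies was set at" p ≤ 0.05.

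Two corrections are planned. For the observational part, "Post-hoc analysis with Bonferroni correction was performed to determine differences between groups". For the experimental part, "Post-hoc analysis with Tukey correction was conducted to assess pre-post exercise significances of dependent variables". As described, the first covers pairs of foot-type groups and the second covers pre-post comparisons, in each case for a given variable.

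The dependent variables are not listed in that section. Neither the Specific Objectives, nor the sample-size text under Design and Sample, nor Statistical Analysis names a primary outcome, a testing order or a rule for success.

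The stated aims differ in strength. Objective 3 is framed "with the objective of establishing the effectiveness of these exercises in improving" the athletes' stability. Objective 4 is softer: "to evaluate possible improvements in sports performance resulting from the exercise program".

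**The concern.** When several outcomes are each tested at 0.05 and any of them may be cited in support of the program, the chance of at least one false positive exceeds 0.05. The planned post-hoc corrections do not address this, because they adjust comparisons inside an outcome and never across outcomes.

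Objective 3 is where this matters most. Its wording invites a conclusion that the exercises work, and one significant sway parameter or one muscle out of many could be presented as that proof. Without a fixed outcome list, a reader also cannot tell how many tests lie behind a reported result.

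**Working it through.** **The plan's own figure.** The sample-size inputs are three groups, alpha 0.05, power 0.80 and f = 0.40. A one-way ANOVA with noncentrality f²N then needs N = 66 (power 0.818; N = 63 gives 0.798). The plan states no required N to compare with this. The selected samples, 35 + 32 + 36 = 103 and 33 + 31 + 33 = 97, both exceed it. The calculation names no outcome and uses alpha for a single test.

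**Counting the outcomes** (Specific Objectives; Measurement of Dependent Variables):

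| Objective | Components | Count |
|---|---|---|
| 3 | 4 sEMG muscles + 7 static parameters + 4 dynamic parameters | 15 |
| 4 | VO₂max and anaerobic threshold (2) + 4 jump parameters + acceleration, step speed, race time (3) | 9 |
| Both | 15 + 9 | 24 |

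The count is not fixed. The static and jump lists are given as examples, and counting the four displacement directions separately gives 26. In the other direction, the objectives themselves name nine quantities: core activity, static stability and dynamic stability (3), plus jump force, acceleration, step speed, race time, VO₂max and anaerobic threshold (6). Objective 1 opens "Compare the average muscular activity at the center of gravity", which could mean one averaged sEMG measure. No composite for static or dynamic stability is defined.

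**Independent outcomes, no true effects.** The chance of at least one false positive among m tests is 1 − 0.95^m:

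- Objective 3, m = 15: 1 − 0.95^15 = 0.537
- Objective 4, m = 9: 1 − 0.95^9 = 0.370
- Pooled, m = 24: 1 − 0.95^24 = 0.708
- Named quantities only: 1 − 0.95^3 = 0.143 (objective 3), 1 − 0.95^6 = 0.265 (objective 4), 1 − 0.95^9 = 0.370 (all nine)

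**Correlated outcomes.** With one pre and one post measurement, the group-by-time F test equals a one-way ANOVA on change scores. Simulation used equicorrelated normal change scores, groups of 33/31/33 and 100,000 replicates:

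| Assumed correlation | 0.3 | 0.5 | 0.7 | 0.9 |
|---|---|---|---|---|
| Objective 3 (15) | 46% | 37% | 27% | 15% |
| Objective 4 (9) | 33% | 28% | 21% | 13% |
| Pooled (24) | 60% | 47% | 32% | 17% |

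The documents do not fix the allocation to control. Two groups of 64 and 33 change the pooled values by about one percentage point.

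**Check on the remedy.** Suppose two primaries are tested with Holm at 0.05 and the other 22 outcomes with a second Holm procedure that does not depend on the first. Under independence the total error is 1 − (1 − 0.0494)(1 − 0.0488) = 0.096. If the 22 are tested only after both primaries succeed, it is 0.049.

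**The case against.** The strongest reply is that the harm is conditional. Family-wise error matters when any single significant result counts as success, and the plan states no such rule. Much of the wording is tentative, and the observational part is called descriptive. This stands in part: for an openly exploratory study, a label would be enough. But the experimental part carries no such label, and objective 3 speaks of establishing effectiveness, so the plan leaves the matter open.

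A second reply is that the numbers rest on assumptions. The parameters are described as measured or recorded, not as each tested. The correlations are assumed, and a single common value across sEMG, sway, oxygen uptake and sprint time is a convenience. The group-by-time test is also an assumption, since the plan does not say which effect answers objectives 3 and 4, and Friedman's test was not simulated. All of this stands, and the percentages should be read as illustrations. It does not remove the omission.

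A reader might infer that 24 outcomes are tested, or at least 18, and that the study therefore has a 71% false-positive rate. The documents do not support that. The lists are open-ended, so 24 is not a ceiling. The objectives name only nine quantities, so 18 is not a floor. Pooling also joins two objectives that ask separate questions. The 71% further requires independence and no true effect on any outcome.

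**Conclusion.** The gap is real: for objectives 3 and 4 the plan fixes neither a primary outcome, nor the outcomes tested, nor any error control across them. Confidence in that omission is high.

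Its size is less certain. If each named parameter is tested once and there are no true effects, the error per objective lies between about 15% and 54% for objective 3 and between about 13% and 37% for objective 4, over assumed correlations from 0.9 down to 0. One test per outcome is a minimum, because a repeated-measures ANOVA can yield time, group and interaction tests. Testing fewer outcomes lowers the figures: with three quantities for objective 3 and six for objective 4, the independence values are 14% and 26%.

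This limits how an effectiveness claim may be read. It does not invalidate the study.

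**What to change.** **If outcome data are unseen:**
- Name one primary outcome for each of objectives 3 and 4, and the single model effect tested (for example group-by-time).
- Test the two primaries with Holm at family-wise 0.05.
- List all other outcomes and report them as exploratory, with 95% confidence intervals and no significance claims; or test them with Holm only after both primaries succeed.

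**If data have been examined** (the methods are written in the past tense, so this must be established):
- Do not choose a primary outcome now.
- List every outcome tested and adjust across them with Holm or a resampling max-T method that uses their correlation; or label them all exploratory and drop the claim of establishing effectiveness.

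**In either case**, label the observational comparisons exploratory.

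**Cost.** This is a wording change if data are unseen. Otherwise it is a re-analysis or a relabelling. There will be fewer nominally significant results. The plan does not fix power for the experimental part. Under an assumed three-group test with N = 97 and f = 0.40, power is 0.94 at alpha 0.05, about 0.90 at 0.05/2 = 0.025 (the strictest Holm step for two primaries) and about 0.67 at 0.05/24 = 0.0021 (the strictest Holm step across 24). Later Holm steps are less strict. If f were 0.25, the values at 0.025 and 0.05/24 would be 0.46 and 0.17, which favors a small number of primaries.
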